3.5.1.2 Analysis of Pharmacodynamic Endpoint(s)

All of the PD measures will be summarized by scheduled visits. Except for the analyses specified in the following of this section, all of the other PD endpoints will be analyzed for the end-of-treatment measure only using similar ANCOVA model as that in the primary analysis. Treatment effect and baseline value (if available) will be added in the model.

[REDACTED]

[REDACTED]

The CV of CGM glucose values over 7 days at each dose level will be analyzed with a 2-sample t-test (assuming equal variance).

The change in percentage of time in hyperglycemia and hypoglycemia over 24 hours from baseline (Day -1) to Day 49 will be analyzed with the Wilcoxon rank sum test.

The percentage of time in hyperglycemia and hypoglycemia over 7 days at each dose level will be analyzed with the Wilcoxon rank sum test.

The morning (type A) and evening (type C) MMTT CGM glucose AUC_{0-2hr} on baseline (Day -1) and Day 49, will be summarized. Their difference and agreement will be analyzed by the paired t-test and the concordance correlation coefficient, respectively. The CGM glucose AUC_{0-4hr} during MMTT on baseline (Day -1), Day 7, and Day 49, and the corresponding plasma glucose AUC_{0-4hr} will be summarized and analyzed in a similar manner.

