
To assess gastrointestinal (GI) tolerability across different titration schedules (Cohorts 1 and 2)
	
 • Percentage of subjects with GI AEs at each dose level • Percentage of subjects with nausea and vomiting from baseline (Day 1) over 7 days of treatment

To assess the effect of MEDI0382 on glucose lowering during different meals and times of the day as measured by continuous glucose monitoring (CGM) (Cohort 1 only)
	
 • Change in glucose AUC_{24h} from baseline (Day -1) to the end of dosing at each dose level (Days 7, 14, 21, 28, and 49) • Change in coefficient of variation (ratio of standard deviation: mean) over 24 hours from baseline (Day -1) to the end of dosing at each dose level (Days 7, 14, 21, 28, and 49) • Change in coefficient of variation (ratio of standard deviation: mean) over 7 days at each dose level (Days 1 to 7, Days 8 to 14, Days 15 to 21, and Days 22 to 28) • Change in percentage of time in hyperglycaemia (defined as > 7.8 mmol/l (> 140 mg/dl) and hypoglycaemia (defined as < 3.0 mmol/l (< 54 mg/dl) from baseline (Day-1) over 24 hours to the end of dosing at each dose level (Days 7, 14, 21, 28, and 49) • Change in percentage of time in hyperglycaemia; (defined as > 7.8 mmol/l or (> 140 mg/dl) and hypoglycaemia (defined as < 3.0 mmol/l or < 54 mg/dl) over 7 days at each dose level (Days 1 to 7, Days 8 to 14, Days 15 to 21, and Days 22 to 28) • Change in glucose AUC_{120min} during a standardised meal in the morning from baseline (Day -1) and at the end of 49 days of treatment • Change in glucose AUC_{120min} during a standardised meal in the evening from baseline (Day -1) and at the end of 49 days of treatment

To characterise the effect of MEDI0382 on glucose lowering and weight versus placebo after 7, 14, and 49 days (Cohort 2 only)
	
 • Percentage change in glucose AUC as measured by a standardised MMTT from baseline (Day -1) after 14 and 49 days • Change in fasting plasma glucose from baseline (Day -1) to the end of 7, 14, and 49 days of treatment • Percentage and absolute change in body weight from baseline (Day 1) to the end of 7, 14, and 49 days of treatment • Change in HbA1c from baseline (Day -1 to the end of 49 days of treatment

[REDACTED]
	
[REDACTED]

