4.8.3.3 Exploratory Analyses

For analyses of the exploratory endpoints (Section 2.3), an ANCOVA model similar to the primary efficacy analysis will be used for continuous endpoints. For proportion-related endpoints, a logistic regression model will be used with fixed effects of treatment and baseline measurement.

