3.5 Exploratory Pharmacodynamic Endpoint(s) and Analyses

3.5.1.1 Pharmacodynamic Endpoint(s)

- [REDACTED]
- Change in CGM glucose AUC_{0-24h} from baseline (Day -1) to the end of each dosing level for titration and treatment (Cohort 1 only)
- Change in coefficient of variation (CV) (ratio of standard deviation: mean) of CGM glucose values over 24 hours from baseline (Day -1) to the end of each dosing level for titration and treatment (Cohort 1 only)
- CV of CGM glucose values over 7 days at each dose level (Days 1 to 7, Days 8 to 14, Days 15 to 21, and Days 22 to 28) (Cohort 1 only)
- Change in percentage of time in hyperglycemia (defined as > 7.8 mmol/l or > 140 mg/dl as measured by CGM) over 24 hours from baseline (Day -1) to the end of each dosing level for titration and treatment periods (Cohort 1 only)
- Change in percentage of time in hypoglycemia (defined as < 3 mmol/l or < 54 mg/dl as measured by CGM) over 24 hours from baseline (Day -1) to the end of each dosing level for titration and treatment periods (Cohort 1 only)

- Percentage of time in hyperglycemia (defined as > 7.8 mmol/l or > 140 mg/dl as measured by CGM) over 7 days at each dose level (Days 1 to 7, Days 8 to 14, Days 15 to 21, and Days 22 to 28) (Cohort 1 only)
- Percentage of time in hypoglycemia (defined as < 3 mmol/l or < 54 mg/dl as measured by CGM) over 7 days at each dose level (Days 1 to 7, Days 8 to 14, Days 15 to 21, and Days 22 to 28) (Cohort 1 only)
- CGM glucose AUC_{0-4hr} during MMTT (type A) on baseline (Day -1) and Day 49 and during MMTT (type B) on Day 7 (Cohort 1 only)
- CGM glucose AUC_{0-2hr} during morning MMTT (type A) on baseline (Day -1) and Day 49 (Cohort 1 only)
- CGM glucose AUC_{0-2hr} during evening MMTT (type C) on baseline (Day -1) and Day 49 (Cohort 1 only)
- The change in insulin AUC_{0-4hr}, glucagon AUC_{0-4hr}, and active and total (the sum of active and inactive GLP-1) GLP-1 AUC_{0-4hr} from baseline (Day -1) to Day 49 (Cohort 1 and 2)
- The change in pre-meal (i.e., time 0 basal/fasting) values of insulin, glucagon, and active and total (the sum of active and inactive GLP-1) GLP-1 from baseline (Day -1) to Day 49 (Cohort 1 and 2)
For Cohort 1 only, the fasting plasma insulin value on Day 7 will also be summarized
- The change in fasting C-peptide from baseline (Day -1) to Day 7 and Day 49 (Cohort 1 only)
- The change in serum beta-hydroxybutyrate concentration from baseline (Day -1) to Days 22 and 49 (pre-dose and 4 hr post-dose) (Cohort 1 only)

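### The 7-day CGM comparisons of CV and time in hyperglycaemia omit an available Day -1 baseline, and the SAP's level does not match the protocol's change

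*SAP*

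**What the plan says.** SAP 3.5.1.1 defines the Cohort 1 7-day endpoints as levels. The first is "CV of CGM glucose values over 7 days at each dose level (Days 1 to 7, Days 8 to 14", continuing with "Days 15 to 21, and Days 22 to 28". The 7-day percentages of time in hyperglycaemia and in hypoglycaemia use the same four windows.

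SAP 3.5.1.2 then gives the tests. For CV: "The CV of CGM glucose values over 7 days at each dose level will be analyzed with a 2-sample t-test", with equal variances assumed. For the percentages: "The percentage of time in hyperglycemia and hypoglycemia over 7 days at each dose level will be analyzed with the Wilcoxon rank sum test". Neither has a baseline term. The same section's default for pharmacodynamic endpoints not singled out is an ANCOVA like the primary one, where "Treatment effect and baseline value (if available) will be added in the model".

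The protocol reads differently. Its synopsis lists "Change in coefficient of variation (ratio of standard deviation: mean) over 7 days at each dose level", and it also words the 7-day percentages as changes, in the synopsis and in Table 2.3-1. For exploratory endpoints, Protocol 4.8.3.3 says "an ANCOVA model similar to the primary efficacy analysis will be used for continuous endpoints". The primary model in Protocol 4.8.3.1 adjusts for the baseline measurement.

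**The concern.** The SAP departs from the protocol twice, without giving a reason: it analyses a level where the protocol names a change, and it drops the baseline adjustment that the protocol sets as the rule. A baseline measure exists. The sensor goes on at about noon on Day -2 (Protocol Table 4.2.2-1, CGM sensor footnote), and SAP 3.5.1.1 already uses Day -1 24-hour CV and percentage of time as baselines for the 24-hour endpoints.

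What is at stake is precision. Cohort 1 has 39 subjects. Any between-subject spread that was already present before dosing stays in the error term, and a chance baseline imbalance goes uncorrected. A lesser issue is the pooled-variance t-test: under 2:1 allocation its error rate is sensitive to unequal standard deviations.

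**Working it through.** **The plan's own figures.** No power or precision is stated for any CGM endpoint. The only stated power for Cohort 1 alone is in SAP 2.4. By noncentral t, 26 v 13, two-sided alpha 0.05:
- Glucose AUC, difference 28, SD 20: 98.0% (stated 97%).
- Body weight, difference 2.3, SD 2.2: 85.0% (stated 85%).

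Both are within 2 points, so the same method is used below.

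**Inputs for the CGM contrast.**
- n = 26 and 13 (SAP 2.4), so N = 39.
- Two-sided alpha 0.10, the SAP 3.1 default, since SAP 3.5 states no other level.
- ρ, the correlation between the Day -1 24-hour value and the 7-day value. This is an assumption shown over a range.
- Reference effect: the one that gives the unadjusted t-test 60% power. This is chosen for illustration.

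**Unadjusted t-test.** The standard error in SD units is √(1/26 + 1/13) = 0.340. An effect of 0.657 SD gives noncentrality 0.657/0.340 = 1.93 on 37 df, which is 60% power.

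**ANCOVA.** Relative variance = (1 − ρ²) × (1 + 1/(N − 4)) = (1 − ρ²) × 36/35, on 36 df. The second factor charges for estimating the covariate slope.

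| ρ | Variance ratio | SE ratio | Power |
|---|---|---|---|
| 0 | 1.03 | 1.01 | 58.9% |
| 0.2 | 0.99 | 0.99 | 60.4% |
| 0.3 | 0.94 | 0.97 | 62.4% |
| 0.5 | 0.77 | 0.88 | 69.7% |
| 0.7 | 0.52 | 0.72 | 83.5% |

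Break-even is where 1 − ρ² = 35/36, so ρ = 1/6, about 0.17.

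**Percentage of time.** This was simulated on a bounded scale (3,000 runs, alpha 0.05, effect with 80% t-test power). Power for Wilcoxon against rank ANCOVA was 77% v 77% at ρ = 0, 78% v 81% at 0.3, 78% v 87% at 0.5 and 76% v 95% at 0.7. Under the null, rank ANCOVA rejected in 4.6% to 6.1% of runs and Wilcoxon in 4.2% to 5.2%.

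**Equal variances.** This was simulated with equal means, 200,000 runs, at nominal 0.10. The SD ratios are assumed.

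| Active SD : placebo SD | Pooled t | Welch t |
|---|---|---|
| 1 : 1.25 | 0.125 | 0.10 |
| 1 : 1.5 | 0.150 | 0.10 |
| 1 : 2 | 0.18 | 0.10 |
| 1.5 : 1 | 0.06 | 0.10 |
| 2 : 1 | 0.05 | 0.10 |

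The error rate rises when the smaller (placebo) arm has the larger spread, which could happen if treatment narrows glucose variability.

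**Availability of a baseline.** About a day and a half lies between noon on Day -2 and the start of Day 1. A full 24-hour Day -1 value can be formed, but a 7-day one cannot.

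**The case against.** **The protocol's change has no defined baseline here.** The synopsis names Day -1 as baseline in the 24-hour items but names none in the 7-day items, and no baseline of equal length can exist. Analysing levels is a reasonable reading, and Protocol 4.8.1 leaves analysis details to the SAP. The 7-day CV also does not appear in the available text of Protocol Table 2.3-1, which may only reflect redaction or text extraction. This stands as a reason for the level. It is no reason to omit the covariate: ANCOVA on a 7-day level with a 24-hour covariate is valid, because the covariate need not cover the same window.

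**The covariate may be weak.** Day -1 is a single, atypical day: an overnight fast, a morning liquid meal with nothing else eaten for 240 minutes, and water only from 1400 to 2000 apart from the 1800 test meal (Protocol 4.3.1.1). This stands, which is why the table includes low correlations. The worst case costs about 1 point of power.

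**Hypoglycaemia.** Protocol 3.1.4.2 reports that spontaneous glucose below 3.0 mmol/L has not been seen in earlier studies. If most values are zero, adjustment adds little. This stands, and the proposed change is limited to hyperglycaemia.

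**Two stronger readings are tempting.** A reader might infer that the unadjusted tests are biased or invalid. They are not: under randomisation the comparison of levels is unbiased, and if treatment leaves the distribution unchanged, the variances are equal and the pooled t-test holds its level. The inflated rates above need equal means with unequal spreads. A reader might also infer that the SAP wrongly leaves out the end of treatment because the last window is Days 22-28, the first of the four weeks at 300 µg. The protocol fixes the same windows. In addition, SAP 3.5.1.2 already analyses the 24-hour CGM measures at end of treatment: AUC and CV by the default baseline-adjusted ANCOVA, and the percentages as change from Day -1 to Day 49.

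**Conclusion.** The point holds as a minor efficiency and consistency matter. For 7-day CV and 7-day time in hyperglycaemia, the SAP leaves out a baseline that the trial collects, that its own default would use and that the protocol calls for. It also analyses a level where the protocol speaks of a change.

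The gain from adjustment rests on the assumed ρ. It is negligible up to about 0.2, roughly 2 points of power at 0.3, 10 points at 0.5 and 23 points at 0.7, from a 60% starting point at alpha 0.10. The error-rate range of 0.05 to 0.18 for the pooled t-test rests on assumed SD ratios and supports only a precaution. The endpoints are exploratory, SAP 3.1 makes no multiplicity adjustment, and the documents tie no decision to them. The primary analysis is unaffected.

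**What to change.** In SAP 3.5.1.2:
- Analyse 7-day CV in each window by ANCOVA with treatment and the Day -1 24-hour CV as covariate. Because of the 2:1 allocation, use a heteroscedasticity-robust standard error in a small-sample form. The simulation above shows the benefit for the Welch t-test without a covariate; the robust ANCOVA version was not simulated.
- Analyse 7-day percentage of time in hyperglycaemia by rank ANCOVA with the Day -1 24-hour percentage as covariate. The Wilcoxon test can stay for hypoglycaemia.
- Reconcile the protocol's change with the SAP's level. State that CGM starts on Day -2, so no 7-day baseline exists, and that the Day -1 24-hour value serves as covariate only.

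The cost is SAP text and code before unblinding, with no new data or visits, plus the risk of about 1 point of power if the single-day baseline proves uninformative.

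Optionally, add a Days 43-49 window. CGM is planned through Day 50 and a new sensor is applied on Day 36, so the data should exist. This would be a new endpoint that the protocol does not list and should be labelled as such.

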2.3 Exploratory Objectives

Table 2.3-1 Exploratory Objectives and Associated Endpoints

Type	Objective	Endpoint
Safety	To assess gastrointestinal tolerability across different titration schedules (Cohorts 1 and 2)	
 Percentage of subjects with gastrointestinal AEs at each dose level Percentage of subjects with nausea and vomiting from baseline (Day 1) over 7 days of treatment
PD	To assess the effect of MEDI0382 on glucose lowering during different meals and times of the day as measured by continuous glucose monitoring (CGM) (Cohort 1 only)	
 Change in percentage of time in hyperglycaemia (defined as > 7.8 mmol/l or > 140 mg/dl) and hypoglycaemia (defined as < 3 mmol/l or < 54 mg/dl) from baseline (Day -1) over 24 hours to the end of dosing at each dose level (Days 7, 14, 21, 28, and 49) Change in percentage of time in hyperglycaemia (defined as > 7.8 mmol/l or > 140 mg/dl) and hypoglycaemia (defined as < 3 mmol/l or < 54 mg/dl) over 7 days at each dose level (Days 1 to 7, Days 8 to 14, Days 15 to 21, and Days 22 to 28) Change in glucose AUC_{120min} during a standardised meal in the morning from baseline (Day -1) and at the end of 49 days of treatment Change in glucose AUC_{120min} during a standardised meal in the evening from baseline (Day -1) and at the end of 49 days of treatment
Efficacy	To characterise the effect of MEDI0382 on glucose lowering and weight versus placebo after 7, 14 and 49 days (Cohort 2 only)	
 Percentage change in glucose AUC as measured by a standardised MMTT from baseline (Day -1) after 14 and 49 days Change in fasting plasma glucose from baseline (Day -1) to the end of 7, 14, and 49 days of treatment Percentage and absolute change in body weight from baseline (Day 1) to the end of 7, 14, and 49 days of treatment Change in HbA1c from baseline (Day -1) to the end of 49 days of treatment

Table 2.3-1 Exploratory Objectives and Associated Endpoints

Type	Objective	Endpoint
PD	To assess the effect of MEDI0382 on ketone bodies, amino acids, and free fatty acid (FFA) levels over 49 days of treatment (Cohort 1 only)	
 Change in plasma beta-hydroxybutyrate from baseline (Day -1) while fasted and at 4 hours postdose after 49 days Change in FFA levels from baseline (Day -1) after 49 days of treatment Change in amino acid levels from baseline (Day -1) after 49 days of treatment

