4.8.3 Efficacy

4.8.3.1 Primary Efficacy Analysis

The efficacy analysis will be based on the ITT population. The coprimary efficacy endpoints of percentage glucose AUC change and percentage weight change from baseline to 49 days (Section 2.1) will be compared between MEDI0382 and placebo arms, using an analysis of covariance (ANCOVA) model, adjusting for treatment and measurement at baseline.

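### SAP 3.5.1.2 gives the morning and evening meal CGM endpoints no comparison of MEDI0382 with placebo; the evening meal response is then tested between arms nowhere

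*SAP*

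**What the plan says.** **Objective.** Protocol 2.3 (Table 2.3-1, Cohort 1 only) states: "To assess the effect of MEDI0382 on glucose lowering during different meals and times of the day as measured by continuous glucose monitoring". SAP 2.1.3 keeps this objective.

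**Endpoints in the protocol.** Under that objective, Table 2.3-1 lists the change in glucose AUC over 120 minutes "during a standardised meal in the morning from baseline (Day -1) and at the end of 49 days of treatment", and the same "during a standardised meal in the evening from baseline (Day -1) and at the end of 49 days of treatment".

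**Analysis in the protocol.** For exploratory endpoints, Protocol 4.8.3.3 says that "an ANCOVA model similar to the primary efficacy analysis will be used for continuous endpoints". In the primary analysis (4.8.3.1) the endpoints "will be compared between MEDI0382 and placebo arms, using an analysis of covariance (ANCOVA) model, adjusting for treatment and measurement at baseline".

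**Endpoints in the SAP.** SAP 3.5.1.1 lists CGM glucose AUC0-2hr "during morning MMTT (type A) on baseline (Day -1) and Day 49 (Cohort 1 only"), with a matching line for the evening Type C meal. These are values on two days; the word change is gone.

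**Analysis in the SAP.** SAP 3.5.1.2 opens with a default: "Except for the analyses specified in the following of this section, all of the other PD endpoints will be analyzed for the end-of-treatment measure only". The default model is an ANCOVA with treatment and baseline. The meal AUCs have their own entry further down the section, so they fall outside that default. They are to be summarised, and then: "Their difference and agreement will be analyzed by the paired t-test and the concordance correlation coefficient, respectively". The text does not say whether this is done by arm or pooled, or on which day.

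**The concern.** The objective asks what the drug does to glucose at each meal. A morning-versus-evening paired t-test asks whether the two meals differ within a person, and a concordance coefficient asks whether two measurements agree. Neither has a treatment term. The concordance coefficient fits the next sentence of the SAP, where CGM and plasma AUC0-4hr are two measurements of the same meal. It fits poorly here: the Type A meal follows an overnight fast and, on Day 49, comes 2.5 hours after dosing, whereas the Type C meal is at 1800 hours after a fast from 1400.

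At stake is the pre-specified answer on the meal part of the objective, above all for the evening. If the comparison is added only after unblinding, it becomes a post hoc choice.

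**Working it through.** The documents give no power, SD or effect size for the meal CGM AUCs, so there is no stated figure to reproduce. The point rests on the text and on what the paired test estimates.

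**1. Which comparisons get a between-arm test**

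| Measure (Cohort 1) | Planned analysis | Between arms? |
|---|---|---|
| CGM 24-hour AUC and 24-hour CV | SAP default ANCOVA, end of treatment | Yes |
| CGM 7-day CV | Two-sample t-test | Yes |
| CGM time in hyper- and hypoglycaemia | Wilcoxon rank sum | Yes |
| Plasma AUC0-4hr, morning Type A meal | Co-primary ANCOVA (SAP 3.4.1.2) | Yes |
| CGM AUC0-2hr, morning Type A meal | Paired t-test, concordance | No |
| CGM AUC0-2hr, evening Type C meal | Paired t-test, concordance | No |

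Protocol 4.3.1.1 specifies no blood sampling at the Type C meal, so no plasma result can stand in for the last row.

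**2. What the paired test estimates**

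Let τ be the evening-minus-morning difference in mean Day 49 AUC under placebo, and let δM and δE be the lowering by MEDI0382 at each meal. The mean evening-minus-morning difference is:

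- placebo arm: τ
- MEDI0382 arm: τ − (δE − δM)
- both arms pooled (26 and 13): τ − (26/39)(δE − δM) = τ − (2/3)(δE − δM)

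If δE = δM, all three equal τ and the drug effect drops out, whatever its size. If δE ≠ δM, the pooled test mixes that difference with τ and cannot separate them. Running the test by arm gives two separate results but no contrast with placebo.

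**3. Simulation (illustration)**

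Assumptions, not from the documents: AUC in SD units, all pairwise correlations 0.5, τ = 0, 26 v 13, 4,000 runs per setting, arms pooled for the paired test. The rejection rates are at two-sided 0.10, the SAP 3.1 default, because SAP 3.5.1.2 states no level.

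| Drug effect, morning / evening | Paired test | ANCOVA morning | ANCOVA evening |
|---|---|---|---|
| 0 / 0 | 10.7% | 10.7% | 10.2% |
| 1.0 / 1.0 SD | 9.2% | 94.9% | 94.9% |
| 1.4 / 1.4 SD | 9.9% | 99.8% | 99.8% |
| 1.4 / 0.7 SD | 86.3% | 99.9% | 75.7% |

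With equal effects the paired test stays at its nominal level. With unequal effects it reacts, but step 4 shows that it also reacts with no drug effect at all.

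**4. A time-of-day difference with no drug effect**

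For a paired t-test on n = 39, the noncentrality is d√39, where d is the time-of-day difference in SDs of the within-subject difference (assumed). For d = 0.3 it is 0.3 × 6.245 = 1.87.

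| d | Rejection at 0.10 | Rejection at 0.05 |
|---|---|---|
| 0 | 10% | 5% |
| 0.1 | 16% | 9% |
| 0.3 | 58% | 45% |
| 0.5 | 92% | 86% |

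**5. What a between-arm comparison could detect**

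Unadjusted two-sample noncentral t, 37 degrees of freedom, standard error SD × √(1/26 + 1/13) = 0.340 × SD. The difference detectable with 80% power is 0.977 SD at 0.05 and 0.860 SD at 0.10.

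| Assumed SD | At 0.05 | At 0.10 |
|---|---|---|
| 15% | 14.7% | 12.9% |
| 20% | 19.5% | 17.2% |
| 30% | 29.3% | 25.8% |

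The 20% is the SAP 2.4 figure for glucose AUC change from baseline, borrowed here. The glucose AUC gap in the earlier study (Protocol 1.4) is 32.8 − 10.2 = 22.6 percentage points. A difference of that size would have 90.0% power at 0.05 and 94.7% at 0.10 with SD 20%, but 57.9% and 70.3% with SD 30%.

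**The case against.** **The paired contrast has a stated purpose.** Protocol 3.2.3.3 says the morning and evening meals are given so that post-prandial excursions at different times of day can be compared, and both meals are one can of Ensure Plus (Table 4.2.2-1, footnotes r and s). This stands. It justifies keeping the paired t-test as a description of time of day, but not using it in place of the drug comparison.

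**The SAP may refine the protocol.** Protocol 4.8.1 leaves further detail to the SAP, and the SAP also uses a t-test and Wilcoxon tests for continuous CGM endpoints. A departure from ANCOVA is therefore not an error in itself. But those substitutes still compare the arms, and this one does not.

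**The arms can be compared by eye.** SAP 3.1 tabulates by cohort and treatment group, so each meal's AUC on Day -1 and Day 49 will appear by arm. This stands as a descriptive contrast, but it is not the analysis in Protocol 4.8.3.3.

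**The morning meal is already tested.** The same Type A meal supplies the co-primary plasma AUC0-4hr. This stands for the drug effect at the morning meal, though with a different measure and window. It does nothing for the evening.

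**A reader might infer that the whole CGM objective lacks a treatment comparison.** The documents do not support that: the 24-hour and 7-day CGM endpoints are compared between arms. The 24-hour measures include the evening but do not isolate the meal.

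**Conclusion.** The concern holds for the two meal endpoints. As written, SAP 3.5.1.2 removes them from the treatment ANCOVA and gives them methods that cannot estimate the effect of MEDI0382 at either meal, pooled or by arm. The gap is complete for the evening meal's own response and partial for the morning meal.

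It is limited in reach: the endpoints are exploratory, and no primary or secondary conclusion, safety assessment or sample size depends on them.

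Two further inferences go too far. The planned test does not always reject at alpha: that is so only if the drug affects both meals equally and there is no time-of-day difference. Nor do the documents show that the replacement would be well powered. The power figures borrow an SD that the plan gives for glucose AUC change in its sample-size section, not for CGM AUC0-2hr, and the 22.6-point difference comes from a 4-hour AUC at up to 200 µg in another study. The conclusion rests on the text and the algebra, not on those figures.

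**What to change.** In SAP 3.5.1.1, define each meal endpoint as the change in CGM AUC0-2hr from Day -1 to Day 49, as in Protocol 2.3.

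In SAP 3.5.1.2:

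- Analyse the morning and the evening change separately by ANCOVA, with treatment and the corresponding baseline AUC.
- Compare arms on the change in the within-subject evening-minus-morning difference. This isolates δE − δM and tests whether the drug effect depends on time of day.
- Keep the paired morning-evening t-test, if wanted, as a supplementary description. State the day and whether it is run by arm or pooled.
- Reserve the concordance coefficient for CGM versus plasma AUC0-4hr.

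The cost is a change of SAP wording and two or three extra model fits. No new data are needed. The change should be made before unblinding.
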